6. TRIAL POPULATION

6.1 Inclusion criteria

- 1. Signed and dated Informed Consent, obtained prior to the inclusion in the trial
- 2. Men and women of any ethnic origin aged 18-75 years
- 3. Women with childbearing potential willing not to start a pregnancy during the course of the study (at least within the time period foreseen for the patch absorption, i.e. 6-8 weeks from the application of Hemopatch)
- 4. Men having relationships with women with childbearing potential willing not to procure a pregnancy during the course of the study (at least within the time period foreseen for the patch absorption, i.e. 6-8 weeks from the application of Hemopatch)
- 5. Patients undergoing liver resection for any underlying disease and with resectable mass. The list of the underlying diseases is the following (but might not be limited to):
 - Hepatocellular carcinoma
 - > Hilar cholangiocarcinoma
 - Adrenal cancer metastasis
 - > Breast cancer metastasis
 - Colorectal cancer metastasis
 - Ovarian cancer metastasis
 - > Biliary carcinoma
 - > Hemangioma
 - > Hepatic adenoma
 - > Focal nodular hyperplasia
 - Unilocular hydatid cyst
 - Multilocular hydatid cyst

6.2 Exclusion criteria

- 1. Trauma surgery
- 2. Active sepsis around the liver
- 3. Documented history of cirrosis
- 4. Pregnant or nursing women
- 5. Severe coagulopathy (defined as an International normalized ratio INR >2.0)
- 6. Severe Liver disfunction, as per clinical assessment
- 7. Previous liver transplantation
- 8. Laparoscopic procedure
- 9. Any other intraoperative finding, which defines the non eligibility of the patient for liver resection
- 10. Known hypersensitivity to bovine proteins or brilliant blue
- 11. Mental condition rendering the patient unable to understand the nature, scope and possible consequences of the study

6.3 Withdrawal procedures

Patients have the right to withdraw from the trial on their request or at the discretion of the Principal Investigator and or his delegates.

The discontinuation from the study is foreseen in the following conditions:

- ✓ patient's request (also not motivated);
- ✓ principal investigator's decision (motivated) if considered as necessary, in own judgment, for the interest of the patient;
- ✓ occurrence of new diseases clinically relevant, not related to the study treatment;
- ✓ occurrence of particularly important adverse reactions;
- ✓ occurrence, in the course of the study, of one or more of the situations listed in the "exclusion criteria".

Patients withdrawn because of Hemopatch's failure, should be monitored for safety until the end of the study (please refer to the section 9.1).

7. STUDY TREATMENT

7.1 Treatment in study

Hemopatch is an EMA approved sealant for hemostasis. It consists of a soft, thin, pliable, flexible pad of collagen derived from bovine dermis, coated with NHS-PEG. The white, tissue-facing side is covered with a thin layer of NHS-PEG that provides firm tissue attachment, thus sealing the bleeding surface and inducing hemostasis simultaneously. Due to its flexible structure, the application of Hemopatch to the site where hemostasis is desired is easily controlled. For differentiation, the non-coated side is marked with blue squares of a biocompatible colorant.

Hemopatch will be supplied in the following size:

Hemopatch 45 x 90 mm

Hemopatch is intended as an haemostatic device for surgical procedures when control of bleeding by pressure, ligature or conventional procedures is either ineffective or impractical.

In contact with blood, collagen induces aggregation of platelets. Platelets deposit in large numbers on the collagen structure, degranulate, and release coagulation factors that, together with plasma factors, enable the formation of fibrin. The structure of Hemopatch provides a three dimensional matrix for the additional mechanical strengthening of the clot. The NHS-PEG coating of this device, when in contact with blood, enhances its tissue adhesion properties and seals the bleeding surface. When applied as recommended, Hemopatch is resorbed in 6 – 8 weeks with little tissue reaction.

Hemopatch is not intended to be used in pulsatile, severe bleedings. The use of Hemopatch is not recommended in the presence of an active infection. Hemopatch is not intended as a substitute for meticulous surgical technique and the proper application of ligatures or other conventional procedures for hemostasis. Hemopatch should be maintained dry prior to application [15].

7.1.1 Application of Hemopatch

The investigator will select the appropriate size of the pad so that it overlaps the margins of the bleeding surface by about 1 cm. The pad may be cut to the desired size and shape. Dry gloves and surgical instruments (forceps, scissors) should be used to handle, cut and apply Hemopatch. Multiple pads may be used for larger bleeding surfaces. The investigator will apply the dry Hemopatch with the non-marked white surface contacting the bleeding area. A dry gauze or patty will be used and will be hold in place with gentle, uniform pressure over the entire pad surface for 2 minutes. When applying Hemopatch, the investigator should minimize contact with bloody surgical instruments, gauzes or gloves due to the affinity of collagen to blood. After 2 minutes, the investigator should gently remove the gauze or patty from the pad; gentle irrigation may also help in removing the gauze or patty without dislodging Hemopatch from the bleeding site. If the bleeding has not been satisfactorily controlled, Hemopatch can be removed, without tissue damage, up to 3 minutes from the time of the initial tissue contact. The investigator should not try to forcefully remove the pad.

The target bleeding site is defined as a bleeding site that, after 30 seconds of firm manual compression, has persistent bleeding requiring immediate attention. The investigator, an experienced hepatic surgeon, will define the bleeding source (arterial, venous, capillary), bleeding severity (oozing, middle or spurting) and the approximate area of bleeding site (cm², mean).

7.1.2 Packaging, storage, labelling and accountability

Hemopatch will be used with size 45X90 mm and will be provided to the site with the standard packaging. Nevertheless, the standard packaging will be specifically labelled in order to comply with the need to trace the assignment to the patient within this clinical trial. The identification of the packages assigned will be managed through the randomization procedure and will be reconciled within the accountability procedures that will be put in place for the purposes of the trial.

7.2 Randomization

A phase IV randomized comparative design with specific statistical tests will be carried out. Patients will be randomly assigned to standard (ARM A) or experimental (ARM B; Hemopatch in addition to common surgical techniques) with a 1:1 ratio. The study endpoint is the time interval to obtain hemostasis.

Assigned treatment ARM will remain unknown to the patients, while physicians will use the treatment assigned according to the randomization list.

The randomization will be performed at the visit 2 - baseline, before surgery. Details on the randomization process managing and possible stratification factors to be considered will be included in a specific document, which will be finalized before the study starting.

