 - During the hospitalization (from day 2 to day 6) the panel of the blood tests could be modified.
- note 3: the assessment of liver function includes: ALT, AST ALP, bilirubin and total protein, gamma-GT,.

 During the hospitalization (from day 2 to day 6) the panel of the liver function could be modified.

- note 4: viral titres include: Hepatitis B and C. Tests to be performed only if not yet available within the medical history of the patient or if the previous results available have to be confirmed. HIV test is performed according to Principal Investigator or his delegates decision.
- note 5: hematology, the assessment of liver function, the determination of the viral titres and the pregnancy test, if applicable, will be evaluated by the Principal Investigator (PI) and/or his delegates and recorded first in the patient's medical record and then in the eCRF. The Principal Investigator and/or his delegates will check the laboratory test results vs. the inclusion/exclusion criteria. In case any result shows an out of range parameter judged to have an impact on the Inclusion/exclusion criteria, this will be repeated before the confirmation for randomization.
- note 6: randomization will be performed by an independent statistician who will maintain it during the entire period of the study.
- note 7: the Principal Investigator and/or his delegates will record, first in the patient's medical record and then in the eCRF, the following information: source of bleeding, bleeding severity using "oozing" or "moderate", approximate area of bleeding.
- note 8: the Principal Investigator and/or his delegates will record, first in the patient's medical record and then in the eCRF, the following information: hepatic parenchyma characteristics, intraoperative measurement of total volume of transfused blood products, duration of the surgery, type of the hepatic resection, the estimated intraoperative blood loss, the use of Pringle's maneuver.
- note 9: the Principal Investigator and/or his delegates will record, first in the patient's medical record and then in the eCRF, the output (in ml) and the characteristics of the perihepatic drains (drain pigmentation, i.e.biliary bloody clear). These information will be recorded by the Principal Investigator and/or his delegates from day 1 after surgery to the End of Study Visit if the drainage is still in place.

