5.2 Visit procedures

Below is a detailed description of each visit planned for the study. The Principal Investigator and/or his delegates will record each information first in the patient's medical record (or appropriate source document) and then in the eCRF.

Visit 1 (Screening): Day -90 to -1

- Informed Consent procedure completion, which has to be implemented before any trial procedures is performed
- Inclusion and exclusion criteria verification and confirmation
- Complete medical history, vital signs (BP, HR) collection and physical examination
- Pregnancy test (by serum or urine determination, according to Principal Investigator or hisdelegates decision) for women of childbearing potential or with amenorrhea ≤ 2 years
- Hematology examinations, which include: glucose, urea nitrogen, , creatinine, sodium, potassium, calcium, total
 cholesterol, HDL and LDL, triglyceride, , alkaline phosphatase, LDH, complete blood cell counts with differential and
 platelet counts, APTT, PT, INR, fibrinogen, VES, PCR
- ECG
- Pulmonary slab. In case the patient has performed a CT scan or RMN (because of the routinary assessment of the progression of the underlying disease) within at least 2 months from the ICF signature, the pulmonary slab will not be performed Liver function test includes: ALT, AST, ALP, bilirubin and total protein, Gamma-GT
- The determination of viral titres include: hepatitis B and C,. Tests to be performed only if not yet available within the medical history of the patient or if the relevant results need to be confirmed. HIV test is performed according to Principal Investigator or his delegates decision
- Concomitant medications recordings
- · Adverse event assessment and recording

Visit 2 (Baseline):- Day 0

- Laboratory test results evaluation
- Check and confirmation of the inclusion and exclusion criteria vs. the laboratory test results
- Randomization of the patient, according to the specific procedure implemented for the study
- Concomitant medications recordings
- · Adverse event assessment and recording

Visit 3 (Surgery):Day 1

- Evaluation of the appropriate target bleeding site in the hepatic parenchyma ("oozing" or "moderate")
- Recording of bleeding site characteristics (source of bleeding, bleeding severity using "oozing" or "moderate", approximate area of bleeding site)
- Recording of intraoperative details (hepatic parenchyma characteristics, intraoperative measurement of total

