 volume of transfused blood products, duration of the surgery, type of hepatic resection, the estimated
 intraoperative blood loss and the use of Pringle's maneuver) Concomitant medications recordings
- Adverse event (intraoperative and not-intraoperative) assessment and recording

The patients randomized to Common Surgical Techniques (CST) will be treated conventionally while the patients randomized to experimental technique (CST + Hemopatch) will be treated conventionally with the adjunct of Hemopatch.

For patients included in ARM B Hemopatch is applied upon the verification made by the surgeon of the presence of an appropriate target bleeding (oozing or moderate) site in the hepatic parenchyma. At the time point of application a stopwatch starts simultaneously (time zero). Time to hemostasis is defined as the time required to obtain successful haemostasis in a single bleeding site. This time will be recorded by the operator delegated by the Principal Investigator and according to the surgeon's observation. At 3 minutes the inspection will be made and, if haemostasis is not

achieved, the treatment is considered failed and the Principal Investigator and/or his delegates is allowed to use additional haemostatic measures (including other topical haemostatic agents).

The time to haemostasis will be recorded before in the patient's medical record and then in the eCRF. The bleeding site will be observed for 1 additional minute (after the first 3 minutes) at the end of the haemostatic procedure and at the end of the surgery, in order to confirm the achievement of haemostasis. At the end of surgery at least one perihepatic Jackson-Pratt drain will be left near the site of resection.

Patients allocated to ARM A, will undergo the conventional hemostatic procedures and therefore also these patients will end up with a perihepatic Jackson-Pratt drain, which will be left near the site of resection.

Visit 4 (+1 day after Surgery): Day 2

- Hematology examinations, which includes: glucose, urea nitrogen, creatinine, sodium, potassium, calcium, total
 cholesterol, HDL and LDL, triglyceride, alkaline phosphatase, LDH, complete blood cell counts with differential and
 platelet counts, APTT, PT, INR, fibrinogen, VES, PCR
- · Liver function test examinations, which include: ALT, AST, ALP, bilirubin and total protein, gamma-GT
- Output (in ml) and characteristics of the perihepatic drains (drain pigmentation, i.e. biliary bloody clear)

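### The protocol randomises before surgery and blinds only the patient, and it does not require the target bleeding site to be recorded before the surgeon learns the arm

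*Protocol*

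**What the plan says.** **Timing of allocation.** Protocol section 7.2: "The randomization will be performed at the visit 2 - baseline, before surgery". The flow chart in 5.1 likewise places randomisation at Visit 2 (Day 0).

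**Blinding.** Section 7.2: "Assigned treatment ARM will remain unknown to the patients, while physicians will use the treatment assigned according to the randomization list".

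**The scored site.** Section 7.1.1: "The target bleeding site is defined as a bleeding site that, after 30 seconds of firm manual compression, has persistent bleeding requiring immediate attention". The same paragraph has the investigator, an experienced hepatic surgeon, define the source, severity and approximate area of the bleeding. Section 11.5 defines time to hemostasis on a single bleeding site.

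**When the site is identified.** The Visit 3 (Surgery, Day 1) list in 5.2 contains "Evaluation of the appropriate target bleeding site in the hepatic parenchyma" and "Recording of bleeding site characteristics", with no restriction to one arm.

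**The order of steps in theatre.** Section 5.2 gives an order for one arm only: "For patients included in ARM B Hemopatch is applied upon the verification made by the surgeon of the presence of an appropriate target bleeding" site. For Arm A it says only that conventional hemostatic procedures are used.

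**Who holds the allocation.** Note 6 to the flow chart: "randomization will be performed by an independent statistician who will maintain it during the entire period of the study". Section 7.2 adds: "Details on the randomization process managing and possible stratification factors to be considered will be included in a specific document", to be finalised before the study starts. That document is not shown.

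**The concern.** Randomisation makes the patients in the two arms comparable. It does not make the bleeding sites comparable if each site is chosen after allocation by someone who may already know the arm. Here the unit on which success is scored does not exist at Visit 2. It comes into being at Visit 3, when the surgeon decides which bleeding point persists after compression, counts it as the target and grades it.

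A surgeon who knew the arm could, without intending to, settle on an easier or a harder site in one arm. Responder proportions would then differ for a reason other than treatment, and the chi-square test in 11.5 cannot tell the two apart. The direction cannot be known in advance. A larger sample would not help, because this is bias and not imprecision.

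**Working it through.** **1. Sequence.** Setting the sections side by side:

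| Step | Visit | Who | Knowledge of arm required by the protocol |
|---|---|---|---|
| Randomisation (5.1, 7.2) | 2, before surgery | Independent statistician (note 6) | – |
| Disclosure of arm to the surgeon | not stated | – | – |
| Compression test and choice of site (7.1.1, 5.2) | 3 | Surgeon | no rule that the arm is still unknown |
| Source, severity, area recorded (5.2, note 7) | 3 | Principal investigator or delegates | no rule that the arm is still unknown |
| Hemostasis judged at 3 minutes (5.2) | 3 | Surgeon's observation | not blinded |

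The gap is in the second row. Section 7.2 fixes when the allocation is made and says that physicians act on it, but no section says when they learn it relative to the third and fourth rows.

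**2. What the existing safeguards do.**
- The compression test sets a threshold for a qualifying site. It leaves a judgement about persistent bleeding, and it does not say which site to take if several qualify.
- Target sites are limited to oozing or moderate bleeding (5.2), which narrows the range.
- Recording source, severity and area in both arms lets an imbalance be seen. It does not prevent one, and the grading may be done by someone who knows the arm.
- The independent statistician protects the list. Nothing is said about the moment of disclosure.

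**3. The plan's own figure.** Inputs from 11.1 and 11.5: 66% v 34%, two-sided 5%, 49 per arm, chi-square test. The pooled proportion is 0.50.
- Standard error under no difference: √(2 × 0.50 × 0.50 / 49) = 0.1010.
- Standard error under the alternative: √(2 × 0.66 × 0.34 / 49) = 0.0957.
- Power = Φ[(0.32 − 1.96 × 0.1010) / 0.0957] = Φ(1.275) = 89.9%. Exact enumeration of the uncorrected chi-square gives 90.5%.

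The stated 98 therefore delivers the stated 90%. The concern is not an arithmetic error in 11.1.

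**4. Illustration of site-choice bias.** The document gives nothing from which a bias could be sized, so the shifts below are assumptions. Suppose there is no treatment effect and the true rate is 34% in both arms, but site choice moves one arm. The exact rejection rate of the two-sided 5% chi-square at 49 per arm is:

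| Rate in the shifted arm | Shift | Rejection |
|---|---|---|
| 34% | 0 | 4.8% |
| 39% | +5 points | 7.8% |
| 29% | −5 points | 8.1% |
| 44% | +10 points | 17.3% |
| 24% | −10 points | 19.1% |

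The table shows how sensitive the test is to a moderate shift. It is not evidence that a shift of any of these sizes would occur.

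**The case against.** The strongest reply is that 7.2 fixes when the allocation is made, not when the surgeon is told. Process details are delegated to a document due before the study starts, and an independent statistician maintains the randomisation. That document could delay disclosure. On this view the protocol is silent on a delegated detail rather than wrong. In part this stands: a reader might infer that the surgeon is stated to know the arm before choosing the site, and the protocol does not say so. But the protocol itself fixes the pre-surgical timing and the patient-only blinding. What it delegates is the management of the process and possible stratification, with no instruction to withhold the arm until the site is recorded.

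A second reply is that site evaluation and recording are listed for all patients at Visit 3, ahead of the treatment narrative, and that the compression test and the severity limit bound the choice. This is correct and reduces the concern. A list of visit procedures is still not a rule that the record precedes disclosure.

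Two stronger readings are tempting and are not supported.
- *The trial-labelled package gives the arm away at Visit 2.* Section 7.1.2 says only that package identification runs through the randomisation procedure. It gives no preparation date, and the flow chart puts device accountability at Visit 3.
- *98 is too few because 98 are both required and enrolled.* The document gives no rate of patients without a qualifying site and does not say that such patients leave both arms. The exclusion named in 11.5 applies to the Hemopatch arm only. With an assumed loss of 5%, 10% or 20% in that arm alone, power is 89.1%, 88.2% or 86.1%, a small change.

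Finally, the fix is partial: the 3-minute assessment still rests on the surgeon's observation. This is so, and it is a reason to protect the step that can be protected.

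**Conclusion.** The point holds as a gap in the design as written. Allocation precedes surgery, only the patient is blinded, the surgeon selects and grades the one scored site afterwards, and no provision puts the site record before disclosure of the arm. The primary comparison is therefore open to site-selection bias, which the existing safeguards limit and can reveal but do not exclude.

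The size of the bias cannot be derived from the document, and the rejection rates above rest entirely on assumed shifts. The conclusion also depends on the separate randomisation document not already delaying disclosure. If it does, the protocol only needs to be aligned with it. There is no case here for recruiting more patients. This is a cheap improvement worth making, not a finding that the trial's result would be invalid.

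**What to change.** Amend 7.2, note 6 (in the synopsis and in 5.1) and the Visit 3 text in 5.2 so that, in both arms, the target site and its source, severity and area are recorded in theatre before the arm is disclosed to the surgeon. Either route works:

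- keep randomisation at Visit 2, with the allocation concealed from the surgeon until that record is made; or
- open the allocation at Visit 3 once the site is confirmed, move the randomisation entry in the flow chart accordingly, and count the 98 patients (49 per arm) from that point.

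The separate randomisation document should state the same order.

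**Cost.** A procedural amendment, and an envelope or web page to be opened in theatre. Patients stay blinded and the sample size does not change. The change protects the selection and grading of the site only; the 3-minute judgement of hemostasis remains unblinded.

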7.3 Concomitant medications

No contraindications to the use of any concomitant medication during the course of the study.

8. VIGILANCE REQUIREMENTS

8.1 Incidents and near incidents

Definitions

Incident

Any malfunction or deterioration in the characteristics and/or performance of a device, as well as any inadequacy in the labeling or the instructions for use which, directly or indirectly, might lead to or might have led to the death of a patient, or USER or of other persons or to a serious deterioration in their state of health.

Fatal incident

Incident where the Medical Device (MD) determined (or contributed to determine) the patient death (or user death). Factors such as potential risks in use of MD, characteristics of MD, patient health condition, etc. should be considered to assess the causality relationship between the MD and the death. The evaluation of the health professional who witnessed the fatal event should be also taken into account.

Incident in which the MD has caused a serious deterioration in the health condition of a patient or user or third person is to be intended as:

- an illness or life-threatening injury;
- > an impairment of a body function;
- > a condition requiring medical or surgical intervention to prevent an impairment of a body function or impairment of a body structure;
- > a condition requiring hospitalization or prolongation of hospitalization.

Near Incident

Near Incident is to be intended as:

- ➤ the condition where any malfunction or deterioration in the characteristics or performances, as well as any inadequacy in the labeling or instructions for use could result, if the MD had been used, a worsening of health condition or death of the patient or user, or
 - the condition where any malfunction or deterioration in the characteristics or performances, as well as any inadequacy or in the labeling or instructions for use could cause during the procedure of use or following, if health personnel had not intervened, a worsening of health condition or death of the patient or user.

Complaint

Health care professionals should report only to the manufacturer or authorized representative or distributor any non-compliance and / or events that are not listed above, concerning the use or pre-use procedures, related to a MD.

Investigator Regulatory Obligations

The Investigator should submit to the Regulatory Authority (Ministero della Salute), to the EC and possibly also to the manufacturer/ authorized representative/distributor every incident and near incident, as defined above. Such submissions must be performed:

- within 10 calendar days by occurrence for incidents;
- > within 30 calendar days by occurrence for near incidents.

The form provided in Appendix I (in Italian) is to be used to report incidents and near incidents. It must be filled in with all the available information, dated and signed.

Upon request by the Regulatory Authorities, the Investigator must complete his report with all available follow-up information.

Reports on complaints must be transmitted to the manufacturer/ authorized representative/distributor within 30 calendar days by event occurrence.

The MD involved in the notified incident/near incident, if still available, must be kept at the Pharmacy of FPG and, unless otherwise specified by Ministero della Salute, delivered to the concerned company within 10 calendar days from the submission date of relevant incident or within 30 calendar days from the submission date of relevant near incident.

Transfer Of Regulatory Obligations

The regulatory obligations are delegated by the Investigator to the Clinical Trial Center – FPG, ACRO Unit. If the Investigator becomes aware of an incident/near incident/complaint as defined above, he must immediately report (not later than 24 hours from the knowledge) to the Clinical Trial Center – FPG by filling in the dedicated form (Appendix I). The form should be compiled in Italian. The reference contacts are reported in the table hereafter.

Clinical Trial Center				
Fondazione Policlinico Universitario A. Gemelli Università Cattolica del Sacro Cuore				
[name]				
FORM Transmission (incident/near				
incident/complaint)				
e-mail	[contact]			
Fax number (to be used just in case of				
electronic mail crash)	[name]			
Contact Person	[name]			
[contact]			
[contact]			
e-mail	[contact]			

Safety Follow-up

The safety information will be recorded starting from the date of the Informed Consent signature by the patient and will end-up at the End of Study Visit. This approach will apply also to those patients who were dropped out from the study because of failure of Hemopatch effect (and therefore treated with a rescue therapy), but who were left Hemoptach on the resection site because of difficulty in removing it. Those patients will be requested to return to the site to perform regularly from Visit 4 to Visit 8.

